Of 445 participants who were classified as either having no evidence of liver disease (n = 335) or nonspecific changes (n= 110) in 2007, 28 (6.29%) participants developed CFLD with portal hypertension by 2017. This comprised 15/110 (13.63%) participants who had NSCFLD and 13/335 (3.88%) participants who has NoLD at baseline in 2007 (risk difference 9.76% 95%C1 3.02-16.49 P<.001). The incidence of CFLD with portal hypertension was 7.51 per 1000 person years of follow-up (95% CI 4.99-10.86). The incidence rate for participants under 10 years of age in 2007 was 10.77 per 1000 person years of follow-up (95% CI 6.97-15.9) compared to 2.13 (95%CI 0.42-6.23) in participants over 10 years of age, incidence rate difference 8.63 (95% CI 3.77-13.55 P<.05). No participant older than 10 years of age in 2007 who was classified as NoLD progressed to CFLD by 2017 (median age at follow-up 22.86 years IQR 5.2). Among 355 participants with NoLD in 2007 13 (3.88%) progressed to CFLD with PH, while 35.5% (119/335) displayed nonspecific evidence of liver disease at follow-up in 2017.

By 2017 18/35 (51.43%) participants with CFLD had died compared to 21/110 (19.09%) with NSCFLD and 32/335 (9.55%) with NoLD (P<.001) Using patient years of follow-up as the denominator, the mortality rate for participants with CFLD was 7.75 (95%CI 4.59-12.25) per 100 person years of follow-up (PYRS), for those with NSCFLD 2.34/100PYRS (95%CI 1.48 – 3.57) and 1.13 /100PYRS (95%CI 0.77-1.59) for those with NoLD. The mortality rate difference between those with CFLD and the combined group of NoLD and NSCFLD was 6.33 (95%CI 2.73-9.3) per 100 PYRS (P<.05). Four participants who developed CFLD during follow-up died, two of whom were under 15 years of age. The median age at death of participants without liver disease was 13.25 (IQR 6.33) years while the median age of death of the 49 participants without liver disease was 13.25 (IQR 5.0) p = NS. Of those with CFLD who died during follow-up 9/18(50%) died from hepatic causes of whom

P.I. [name] 4/8 received a liver transplant while 8/18 (44.4%) died from pulmonary causes. By combining the liver-specific focus of the ILSCFLD with ENHANCE the power to elucidate the effects of the CFTR modulators on CFLD is greatly enhanced.

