In exceptional circumstances where baseline clinical data has been collected prior to the start of treatment either through clinical care or ethically approved research projects (including a cohort of subjects initially recruited to this study on the understanding that it was a non-regulated observational study) subjects already receiving ETI may be recruited to this study and undergo on-treatment visits. Any additional patient data can only be added with written informed consent from the patients/parents concerned.

P.I. [name]

All subjects must have a signed informed consent form and/or signed assent form when appropriate, as determined by the subjects age and individual site and country standards.

Male and female participants of childbearing potential must agree to adhere to contraception requirements as detailed in the local ETI SmPC and in line with the standard of care.

Exclusion criteria

Patients not willing to comply with study procedures or assessments.

Individuals on clinical trials of investigational CFTR modulators.

Clinical instability at baseline assessments. Subjects undergoing an active exacerbation and at the beginning of their treatment should be excluded from the study as this is likely to skew the data.

Any contraindication to ETI treatment as per the local approved SmPC.

Severe hepatic impairment.

Pregnant and breastfeeding women.

Inclusion and Exclusion Criteria for Extension Study

Inclusion criteria

Children and adults with CF who have completed two years participation on the parent study, and are willing to provide informed consent for continued data and bio-sample collection for a period of five years.

Exclusion criteria

Participants not willing to comply with study procedures or assessments.

Individuals on clinical trials of investigational CFTR modulators.

Drug Interruption or Discontinuation of ETI

If a patient experiences a drug interruption, discontinues ETI and/or is prescribed TEZ/IVA, LUM/IVA or IVA, they can continue trial participation.

Advanced Testing v Standard Testing for the Parent Study

As outlined in Table 5, we will have a standard and advanced testing group for the parent study. In addition to all elements of the standard testing group, the advanced testing group will undergo:

- Ultra-low dose spirometry-controlled CT scanning
- Sputum collection
- Nasal lavage collection

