AST	Normal	1-2xULN	2-3xl	JLN	3-5xULN	>5xULN		
ALT	Normal	1-2xULN	2-3xl	JLN	3-5xULN	>5xULN		
ALP	Normal	1-2xULN	2-3xl	JLN	3-5xULN	>5xULN		
GGT	Normal	1-2xULN	2-3xl	JLN	3-5xULN	>5xULN		
PLT		Integer						
РТ		Integer						

Figure 7. RECOVER CFLD worksheet for the Parent Study.

Liver Function Test

Liver function test results (AST, ALT, GGT, ALP, Bilirubin, albumin) will be collected from medical notes prior to drug initiation, 3 monthly for the first year for the parent study and annually thereafter for the remainder of the parent study and the extension study (this is a mirror of the requirements put in place by the health service for sites in ROI when all previous CFTR modulator therapies were introduced). For UK sites LFTs results will be collected from medical notes in accordance to required schedule of collection based on drug approval and funding. The following data from annual labs will be entered into the eCRF: Hemoglobin, hematocrit, platelets, white cell count, prothrombin time. The mean levels, and incidence of elevations of AST or ALT to greater than specified multiple (1-2xULN, 2-3xULN, 3-5xULN and >5xULN) times the upper limit of normal will be compared between those on ETI and (1) their liver function tests in the 2 years prior to starting ETI and (2) age matched historic (modulator naïve) controls from within the last 5 years.

P.I. [name]

Ultrasound

As per routine clinical practice in most centers, people with CF from 6 years of age onwards will have annual liver ultrasound scans as part of annual assessment. In centers where this is not the case, ultrasound scans will be performed for the purposes of the study. Ultrasound scans will be performed using a proforma schedule for reporting the findings including liver texture, the presence of nodules and liver edge irregularity and spleen size with reported measurement of AP length (figure 5). The presence of abnormal liver echotexture, evidence of retrograde portal venous flow and spleen size will be compared between those on ETI and (1) their liver ultrasounds, where available, in the 2 years prior to starting ETI and (2) age matched historic CF (modulator naïve) controls from within the last 5 years (Irish sites).

End of parent study assessment

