At the end of the parent study, the liver disease status of participants (CFLD, non-specific [NSCFLD] and No LD) will be updated based on study assessments and review of study worksheets. Proportions of subjects in each group will be compared before and after modulator therapy in addition to determining how many individuals from each given group move to another group on ETI. This will be compared to historic natural history data from the ILSCFLD study for ROI participants.

Classification as part of extension study

Classification will be assigned to each participant as having CFLD, NSCFLD or NoLD annually during the extension study as above.

Specific Aim 6 for Parent Study and Extension Study – Pulmonary Exacerbations and Antibiotic Use

IV Antibiotic Therapy

The number of courses of IV antibiotics (hospitalizations and home IVs) and their indication (elective or unplanned) will be recorded over the duration of the study. This data will be collected in conjunction with clinical staff at local sites. The number (and number of days) of IV antibiotic courses over the length of the study timeframe will be compared with the number of IV antibiotic courses (and days) in the five years prior to commencement of ETI. Some individuals will have started on previous generations of CFTR modulators in the two to three years prior to the initiation of ETI, in which case data will be available for IV antibiotic courses before and on previous CFTR modulator therapy as well as on ETI.

Oral Antibiotic Use

The number of courses, total number of days and type of oral antibiotics will be collected from pharmacy records submitted with parent/guardian consent (and ethical approval) at the end of the study period as part of the adherence arm of RECOVER. The number of courses and number of days of oral antibiotic use will be documented in the eCRF. Given the complexity of the system at UK sites for collection of this information, data on oral antibiotic use from community pharmacies will be collected only from sites in Ireland.

Analysis of Data

Given the depth of information collected through RECOVER we will be in a position to compare antibiotic use to pulmonary outcome measures such as lung function, structure and inflammation, and non-pulmonary indices such as sweat chloride and medication adherence.

Definition of Exacerbation

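### Two-year liver status changes are set against ILSCFLD history without aligning follow-up time or age, and the incidence of AST/ALT elevation is compared across test counts that are not equalised

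*Protocol*

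**What the plan says.** **Liver status.** Under Specific Aim 5, End of parent study assessment, each participant is classed as CFLD, non-specific (NSCFLD) or no liver disease (NoLD). The measure is then fixed: "Proportions of subjects in each group will be compared before and after modulator therapy", together with the number who move from one class to another on ETI. The external comparator follows: "This will be compared to historic natural history data from the ILSCFLD study for ROI participants". No rate, follow-up alignment or age alignment is stated. In the same aim, the historic controls for liver function tests and for ultrasound are described as age matched.

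**What ILSCFLD is.** Preliminary Results, CF Liver Disease, describes a cohort enrolled under age 18 in 2006–8, assessed in 2006/8, 2011/2 and 2016/17, with a median follow-up of 10 years. Among 445 participants with NoLD or NSCFLD in 2007, "28 (6.29%) participants developed CFLD with portal hypertension by 2017". The overall rate was 7.51 per 1000 person-years. It was 10.77 in those under 10 in 2007, "compared to 2.13 (95%CI 0.42-6.23) in participants over 10 years of age". Of 335 with NoLD, 119 (35.5%) had non-specific disease in 2017.

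**Liver function tests.** The Liver Function Test section compares "The mean levels, and incidence of elevations of AST or ALT to greater than specified multiple" of the upper limit of normal on ETI with two references: the participant's own tests in the two years before ETI, and age-matched modulator-naïve controls. On ETI the parent-study tests fall at months 3, 6, 9, 12 and 24 (Table 14). UK sites follow their own schedule.

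**The concern.** A proportion changing class depends on how long people are watched. RECOVER watches for two years and ILSCFLD for about ten. If the two sets of proportions are compared as written, RECOVER will show less progression even if ETI does nothing to the liver. Progression to CFLD with portal hypertension also fell steeply with age in ILSCFLD, and Table 6 plans 137 of 254 participants (54%) aged 12 or over. Converting to rates therefore removes only part of the gap for that transition.

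The elevation endpoint has a related weakness. If incidence is read as ever elevated, more tests find more elevations at the same underlying risk.

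Preliminary Results says the study will be able to test whether CFTR modulation improves indices of CFLD. Either comparison could influence that conclusion with no drug action behind it.

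**Working it through.** **1. Reproducing the ILSCFLD figures**
- Progression: 28/445 = 6.29%.
- Person-years: 28/0.00751 = 3728, or 3728/445 = 8.4 years per person.
- Age strata: 25/0.01077 = 2321 and 3/0.00213 = 1408 person-years. Together, 28 events in about 3730 person-years gives 7.51 per 1000. The 25/3 split of events is inferred from the stated rates and intervals.
- Exact Poisson 95% intervals: 4.99–10.85, 6.97–15.90 and 0.44–6.22. Stated: 4.99–10.86, 6.97–15.9 and 0.42–6.23.
- Cross-check from the mortality rates: 32/0.0113 + 21/0.0234 = 3729 person-years.

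**2. Follow-up time, no drug effect, constant hazard**

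Two-year risk = 1 − (1 − P)^(2/T), or 1 − exp(−2 × rate).

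| Transition | ILSCFLD | Two-year equivalent |
|---|---|---|
| To CFLD with portal hypertension, T = 10 | 6.29% | 1.29% |
| Same, T = 8.4 | 6.29% | 1.54% |
| Same, from 7.51 per 1000 | – | 1.49% |
| NoLD to non-specific, T = 10 | 35.5% | 8.4% |
| Same, T = 8.4 | 35.5% | 9.9% |

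At T = 10 the unaligned ratios are 1.29/6.29 = 0.21 and 8.4/35.5 = 0.24.

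The protocol names no test. As an illustration, take a two-sample test of proportions at two-sided 0.05 with 75–150 RECOVER participants at risk (assumed). It would declare a false benefit in 36–74% of repetitions for the first transition and in over 99.9% for the second.

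**3. Age (CFLD with portal hypertension only)**
- 2.13/7.51 = 0.28, or 72% lower.
- Carrying only the interval of the older stratum: 0.42/7.51 = 0.06 and 6.23/7.51 = 0.83, so 17–94% lower.

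**4. How many events to expect**

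The protocol does not give the number of Republic of Ireland (ROI) participants at risk. If all 254 were in ROI and at risk (508 person-years), 508 × 7.51/1000 = 3.8 events would be expected at the all-age rate and 508 × 2.13/1000 = 1.1 at the older-stratum rate. The real number at risk is smaller.

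**5. Liver function tests**

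P(at least one elevation in k tests) = 1 − (1 − p)^k for independent tests. With within-person correlation ρ, a beta-binomial gives 1 − B(a, b + k)/B(a, b), where a = p(1 − ρ)/ρ and b = (1 − p)(1 − ρ)/ρ. The per-test risk p and the comparator test counts are assumptions. Two tests corresponds to annual testing, which the protocol calls normal care for the extension.

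| Tests, ETI v comparator | ρ | p = 5% | Ratio | p = 10% | Ratio |
|---|---|---|---|---|---|
| 5 v 2 | 0 | 22.6% v 9.8% | 2.32 | 41.0% v 19.0% | 2.16 |
| 5 v 2 | 0.5 | 11.0% v 7.4% | 1.49 | 21.0% v 14.5% | 1.45 |
| 5 v 4 | 0 | 22.6% v 18.5% | 1.22 | 41.0% v 34.4% | 1.19 |
| 5 v 8 | 0 | 22.6% v 33.7% | 0.67 | 41.0% v 57.0% | 0.72 |

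With equal counts the ratio is 1.

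**The case against.** **Alignment may be supplied elsewhere.** The comparator is named in one sentence, and a separate analysis plan could add detail. Statistical Analysis foresees mixed models with demographic covariates and logistic or multinomial regression. The Collaborators section says the liver group will match its participants to RECOVER's, and the liver examination section foresees longitudinal use of ILSCFLD data. These points have some weight: the text does not say outright that ten-year proportions will be tested against two-year ones. But general covariate models and record matching do not align follow-up or age between the cohorts, and the measure that is written is proportions and counts. If each person's own earlier record is meant, that history is still at a younger age and on roughly five-year spacing. Most 6–11-year-olds, starting about a year after the 2020 approval, would have been born after the 2006–8 enrolment.

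**Stronger readings that the documents do not support**
- *That RECOVER's exclusion criterion, "Severe hepatic impairment", explains part of the gap.* The ILSCFLD rates come from 445 people with NoLD or NSCFLD at baseline, so baseline CFLD is already outside the denominator.
- *That 2.13 per 1000 is the expected rate in the 12+ cohort.* The strata are age in 2007, not attained age, and the older one holds about three events.
- *That the age gradient covers all class changes.* It is reported only for CFLD with portal hypertension. None is given for NoLD to non-specific.
- *That the test comparison is biased towards ETI harm.* The pre-ETI test count is not given. Three-monthly testing accompanied earlier modulators in ROI, and some participants started those two to three years before ETI. Incidence is also not defined as ever elevated, and mean levels are not affected in this way.

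**Weight.** Liver measures are secondary outcomes without a power claim, and the first status comparison is within the cohort, before against after ETI. This limits the consequence but does not remove it.

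**Conclusion.** The point stands for both comparisons, more firmly for the first.

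**Liver status.** Followed as written, the ILSCFLD comparison can show a benefit with no drug action: about 1.3–1.5% against 6.29% for CFLD with portal hypertension, and about 8.4% against 35.5% for NoLD to non-specific. Both rest on a constant hazard. The second also treats status in 2017 as a one-way transition; if non-specific changes come and go, the two-year figure could be higher. For CFLD with portal hypertension, age adds a further difference in the same direction, imprecisely estimated.

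**Liver function tests.** The incidence of elevations depends on test frequency. If comparators were tested annually, ever elevated would be inflated on ETI about 1.5- to 2.3-fold; with four prior tests the ratio is about 1.2, and with eight it reverses. The dependence is established, the direction is not. Annual testing is most plausible for the modulator-naïve controls, because the three-monthly schedule is tied to the introduction of modulators.

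This should be changed before analysis, but it does not touch the primary outcome.

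**What to change.** **Liver status.** For ROI participants at risk (NoLD or NSCFLD at baseline), compare transitions per person-year with ILSCFLD. Standardise the expected number by baseline class and attained-age band, using ILSCFLD individual data; the published strata by age in 2007 are not enough. Report observed/expected with an exact Poisson confidence interval and label it descriptive, because very few progressions are expected. No participants need be removed for the hepatic exclusion for these rates.

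**Liver function tests.** Define the endpoint as the per-test probability of elevation, fitted with a logistic mixed model with a participant effect. Alternatively, use annual-assessment tests only. Apply the same rule to ETI, pre-ETI and control periods, and report the number of tests per person in each.

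**Cost.** This changes the analysis text and needs no new visits or samples, but it does need individual records from the ILSCFLD collaborators. The intervals will be wider, and restricting to annual tests would use fewer of the liver results collected.

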PRAGMA-CF	Perth-Rotterdam Annotated Grid Morphometric Analysis for CF					
PBS	Phosphate Buffered Saline					
QALY	Quality-Adjusted Life-Years					
RV	Residual Volume					
GST	Guy's and St Thomas' NHS Foundation Trust					
SHIELD CF	Study of Host Immunity and Early Lung Disease in CF					
TLC	Total Lung Capacity					
WOCBP	Women of Childbearing Potential					

HYPOTHESIS AND SPECIFIC AIMS FOR PARENT STUDY

Hypothesis

- a. Use of ETI in routine clinical practice is associated with significant and sustained improvements in airway, liver and gastrointestinal outcomes and quality of life in children and adults with cystic fibrosis.
- b. Adherence to routine therapies will decrease after initiation of ETI

Specific Aims

- 1. To determine the effect of treatment with ETI on pulmonary function (FEV1 and LCI) in children and adults with CF over a period of 2 years.
- 2. To determine the effect of treatment with ETI on spirometry-controlled CT scores in children and adults with CF over a two-year period.
- 3. To determine the effect of treatment with ETI on airway infection and inflammation in children and adults with CF
- 4. To determine the effect of treatment with ETI on nutrition, gastrointestinal symptoms, gut inflammation and pancreatic function in children and adults with CF over a two-year period
- 5. To determine the effect of treatment with ETI on CF liver disease in children and adults with CF over a two-year period.
- 6. To determine the effect of treatment with ETI on antibiotic treatment of pulmonary disease in children and adults with CF over a two-year period
- 7. To assess the impact of the introduction of ETI on adherence with overall medical treatments for CF

HYPOTHESIS AND SPECIFIC AIMS FOR EXTENSION STUDY

Hypothesis

a. Use of ETI in routine clinical practice is associated with significant and sustained improvements in airway, liver and gastrointestinal outcomes and quality of life in children and adults with cystic fibrosis.

Specific Aims

- 1. To determine the longitudinal effect of ETI on pulmonary function (FEV1 and LCI) in children and adults with CF over an additional period of 5 years.
- 2. To determine the longitudinal effect of ETI on spirometry-controlled CT scores in children and adults with CF over an additional period of 5 years
- 3. To determine the effect of treatment with ETI on airway infection and inflammation in children and adults with CF.

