The CFQ-R treatment burden subscale, part of the CFQ-R questionnaire, has been used to assess treatment burden in people with CF(113). The treatment burden subscale, which comprises 3 questions, is scored on a standardized 0- to 100-point scale with lower scores representing a higher treatment burden. The questions are as follows: to what extent do your treatments make your daily life more difficult? How much time do you currently spend each day on your treatments? How difficult is it for you to do your treatments each day? CFQ-

Medication Possession Ratios

protocol in table 14.

MPR will be calculated using pharmacy records. MPR is calculated on the basis of the supply of medications for a given period divided by the time in that period. For example, if three scripts for 3 months of a treatment are given over a timeframe of one calendar year, the MPR would 0.75. MPR will be calculated for each individual medication for each study participant. Study consent will be sought for dispensed reports from hospital pharmacy, community pharmacy and homecare providers and GP medical records to be submitted to the subject's center at the end of the study period. Records will be analyzed locally and data on antibiotic use, enzyme use and MPRs per 6-month period calculated by the local study team before being uploaded in an anonymized fashion to the study database.

Qualitative Assessment

Using a combination of previously published data(146), adherence theory (e.g. WHO five dimensions of adherence) as well as the findings of the observational research, a semi-structured interview guide will be designed. Using the same cohort invited to participate in the MEMS component of the study, 20-40 participants will be interviewed with interviews halted when data saturation is achieved. Only subjects from the Dublin centers will be invited to participate for ease of access (the adherence lead for RECOVER is based in Dublin). These data will be analyzed using a qualitative analysis plan involving phenomenography/thematic analysis with constant comparative analysis to the WHO adherence framework. Through this process we hope to be able to explore the experiences of patients/parents on commencement of CFTR modulator and adherence to CF regimens. We hope to be able to establish individual factors that influence adherence in this 'new world' for this large cohort of people with CF.

Data Analysis

Analysis of data will be conducted as follows based on our key research questions:

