• What level of adherence with ETI is seen in the real world?

Measures of weekly adherence (using the three measures independently) will be reported and compared to previously published data on adherence rates with Ivacaftor(115, 147). Adherence over time, using all three methods, will be reported in a weekly fashion as treatment progresses. Changes in adherence over time (weekly, quarterly) will be assessed per individual and cross sectionally. We will explore the relationship between weight gain and subsequent adherence to ETI (because of concerns on behalf of some PWCF about excessive weight gain on modulators).

• Does adherence with other CF therapies decrease after ETI?

Adherence rates, using MPR and self-reported adherence, to medications individually and in groups (vitamins, mucolytics, nebulized antibiotics etc.) will be collected from 3 months prior to the introduction of ETI. The absolute change in adherence for 4 quarters (one before and three after) will be compared using chi squared and ANOVA. The rate of change of weekly adherence will be compared prior to and in the 9 months after (in 3 quarters) initiation of ETI using ANCOVA.

• Does poor adherence adversely affect outcomes?

This question will be addressed from the point of view of firstly, adherence with ETI, and secondly, adherence with other groups of medications. Medium term effects will be determined by comparing overall 12 and 24-month MPRs for given medications and groups of medications and specific relevant outcome measures such as CT scores, LCI, FEV1, nutritional status, antibiotic use and exacerbations at the end of 12 and 24 months respectively.

• Is adherence related to treatment burden?

Results from the various adherence measures will be compared, within individuals, to the CFQ-R treatment burden subscale results at each timepoint.

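### Comparing overall MPR with outcomes at the end of the same 12- or 24-month window cannot separate the effect of adherence from the effect of ETI response on later adherence

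*Protocol*

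**What the plan says.** The data analysis text for Specific Aim 7 of the parent study poses the question "Does poor adherence adversely affect outcomes", first for ETI and then for other groups of medication. The method is stated: "Medium term effects will be determined by comparing overall 12 and 24-month MPRs for given medications and groups of medications and specific relevant outcome measures", with CT scores, LCI, FEV1, nutrition, antibiotic use and exacerbations as examples, taken "at the end of 12 and 24 months respectively".

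On weight, the text says "We will explore the relationship between weight gain and subsequent adherence to ETI" and gives the reason as "because of concerns on behalf of some PWCF about excessive weight gain on modulators". It names no model.

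Four other places bear on this:
- Parent-study hypothesis (b): "Adherence to routine therapies will decrease after initiation of ETI".
- Medication Possession Ratios section: "MPRs per 6-month period calculated by the local study team".
- Statistical Analysis: linear mixed models adjust for demographic and co-morbidity variables. Earlier adherence and response to ETI are not named.
- The limitations paragraph that closes Aim 7: it covers measurement error and incomplete pharmacy records, but not the possibility that outcome influences adherence.

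**The concern.** The MPR comparison fixes three things: a causal question, an exposure summed over the whole window, and an outcome read at the end of that window. Part of the exposure therefore accrues after the person has begun to respond to ETI. If response alters how much of the other treatment is collected, the association mixes two directions of influence. Adjusting for the pre-ETI value does not help, because the response comes after baseline.

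The weight analysis has a related problem. Earlier ETI adherence may raise weight and may also predict later ETI adherence. The word 'subsequent' puts the two variables in time order but does not hold earlier adherence constant.

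The Treatment Adherence background says the authors know of no published longitudinal study of CFTR modulators and adherence to CF regimens. A result with the wrong sign on whether reduced use of other therapies matters would have little beside it to correct it.

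**Working it through.** The protocol states no power or effect size for these analyses, so there is no figure to reproduce. The check covers timing, then algebra under assumed links. All variables below are standardised and all path strengths are assumptions.

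**1. Timing.** Months 6-12 are 6/12 = half of the 12-month MPR window. Months 6-24 are 18/24 = three quarters of the 24-month window. Table 3 (ages 12 and over) gives these means at baseline, 6 and 12 months:
- LCI: 12.21, 10.14, 9.85. Share of the 12-month change seen by month 6: (12.21 - 10.14)/(12.21 - 9.85) = 2.07/2.36 = 88%.
- ppFEV1: 83.65, 91.73, 92.11. Share: 8.08/8.46 = 96%.

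These are group means with differing numbers (LCI n = 82, 83, 49). They show that much of the exposure window follows a visible mean response. They do not show individual trajectories.

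**2. MPR and outcome, other therapies.** Let R be response to ETI, O other-therapy adherence over the window and Y the outcome (higher is better). Take Y = 0.20·O + 0.5·R + error. The unadjusted slope of Y on O is then 0.20 + 0.5·corr(O, R).
- No feedback, no shared trait: 0.20.
- Response lowers O by 0.2: 0.20 + 0.5(-0.2) = 0.10.
- Response lowers O by 0.4: 0.20 + 0.5(-0.4) = 0.00.
- No feedback, but a shared adherence trait with loading 0.6 on both ETI and other-therapy adherence, and ETI adherence raising R by 0.3: corr = 0.3 × 0.6² = 0.108, so 0.20 + 0.054 = 0.25.
- The same trait with feedback of -0.2: 0.15 (by simulation).

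The planned comparison thus returns 0.00 to 0.25 for a true 0.20. With no true effect, subtract 0.20 throughout: -0.20 to +0.05. In simulation (n = 400,000), adjusting for R brought the slope back to about 0.20 in every scenario.

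**3. Lagged alternative.** A separate simulation had 200 participants, no true MPR effect and feedback of 0.2 to 0.4, with and without a shared trait. Same-window slopes ran from -0.19 to +0.09. The slope of later change on earlier MPR, adjusted for the outcome at the start of the interval, stayed between 0.00 and +0.02.

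**4. Weight gain and later ETI adherence.** Let a be the effect of earlier adherence on weight gain, ρ the persistence of adherence, and -0.10 the true effect of weight gain. Take a = 0.2 to 0.4 and ρ = 0.5 to 0.7.
- Outcome is the level of later adherence: slope = aρ - 0.10. Lowest 0.2 × 0.5 - 0.10 = 0.00; highest 0.4 × 0.7 - 0.10 = +0.18.
- Outcome is the change in adherence: slope = -0.10 - a(1 - ρ). Mildest -0.10 - 0.2 × 0.3 = -0.16; strongest -0.10 - 0.4 × 0.5 = -0.30.
- With earlier adherence as a covariate, the slope is -0.10 in both cases.

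The protocol plans both adherence levels and within-person changes in adherence, so either version could be run.

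**The case against.** A reader might infer that weight gain will look harmless to ETI adherence and that giving up other therapies will look harmless to outcomes. The protocol does not support that reading:
- It gives no strength for any of these links.
- Hypothesis (b) predicts a fall in adherence, not a larger fall in better responders. A uniform fall leaves the slope unbiased.
- The 6- v 12-month p-values in Table 3 (LCI 0.3187, ppFEV1 0.7356) are non-significant, which does not show that the gain is complete. BMI z-score in the same table does move between those visits (p = 0.0484).
- A shared adherence trait pushes the MPR slope the other way, and analysing change in adherence exaggerates the weight effect instead of hiding it.
- Weak links leave harm visible. With a true weight effect of -0.30, persistence 0.3 and an adherence-to-weight effect of 0.1, the unadjusted slope is still -0.27.

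It is also fair to say that the weight sentence is exploratory, that its model may sit in an analysis plan not shown, that the named covariates are not declared a closed list, and that adherence is a secondary outcome.

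Finally, lagging has its own cost for ETI. If most of the ETI effect appears by month 6, conditioning on the month-6 outcome removes most of it and could make poor ETI adherence look unimportant.

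All of this stands as a limit on direction, size and remedy. It does not remove the core point, because the exposure window, outcome time and causal question of the MPR comparison are fixed in the protocol.

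**Conclusion.** The point holds as a limit on interpretation. The same-window MPR comparison cannot tell the effect of adherence from the effect of ETI response on later adherence, and the named covariates do not address this. Neither the sign nor the size of the bias can be derived from the protocol; the ranges above only illustrate it under assumed links. The MPR comparison carries the point. The weight analysis is the weaker half: it needs one covariate, since without it the bias depends on whether level or change is modelled. The conclusion rests on response influencing later adherence to some degree, and on adherence persisting within a person. Both are plausible, but neither is quantified in the protocol.

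**What to change.** Amend the Aim 7 data analysis text as follows.

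(a) **Other CF therapies.** Use the 6-month MPRs already planned. Relate MPR in months 0-6 to the change in LCI and FEV1 from month 6 to 12, and MPR in months 0-12 to the change in LCI, FEV1 and CT from month 12 to 24. Adjust for the outcome at the start of each interval and for ETI adherence. Keep the same-window comparison beside it, reported as association.

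(b) **ETI.** Keep the same-window comparison, adjusted for the pre-ETI outcome value and reported as association. A lagged version can serve as a sensitivity analysis.

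(c) **Weight.** Model ETI adherence in the next period on the change in weight or BMI z-score, with ETI adherence during the weight-gain period as a covariate.

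The schedule in Table 14 supplies the data: LCI at 6, 12 and 24 months, three-monthly FEV1 and weight, and CT at 12 and 24 months in the advanced testing group. The cost is a little more analysis work. The lagged analysis does not capture early effects, and its CT part is confined to the advanced group.
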